### **3.5 AVAILABILITY**

MyaLept (Metreleptin) is being supplied by Amryt Pharma PLC.

### **3.6 INITIAL DRUG SHIPMENT AND RE-SUPPLY**

A signed and completed Drug Request Form must be faxed, at least **10 days** prior to the expected delivery date, to **the Medical Affairs Representative**. Used as well as unused vials of expired Metreleptin should be destroyed at the site. We will provide copies of copies of all drug tracking and reconciliation logs as well as proof of destruction at the end of the study to Amryt Pharma.

## **4. POTENTIAL RISKS WITH THE STUDY:**

The overall risks of the study can be divided into risks associated with the evaluation methods and risks associated with recombinant leptin therapy. These risks are balanced against the potential benefits of therapy to participants and the knowledge gained from the study.

### **4.1 RISK ASSOCIATED WITH EVALUATION METHODS**

Risks with blood tests: The total amount of blood drawn from the patients will be kept within the IRB restrictions. Total amount of blood to be drawn with the outlined studies is estimated not to exceed 960 cc over the course of 12 months. Each blood draw is associated with pain and risks of infection though these risks are minimal.

Risks with study procedures: In this study, patients are asked to have 2 extensive visits in 12 months. In addition to the above risks some patients may find the time needed to complete the research studies an inconvenience in their routine lives. Each participant into the study will clearly understand that participation is totally voluntary.

Our research plans will be monitored by the University of Michigan IRB.

### **4.2 RISKS ASSOCIATED WITH TREATMENT WITH RECOMBINANT HUMAN LEPTIN**

General: Hypoglycemia was the most frequent treatment-emergent adverse event reported in two previous clinical studies in 29 subjects with lipodystrophy. Metreleptin has been shown to have an antidiabetic effect in lipodystrophic patients. The investigators will monitor subjects with diabetes and consider adjustments to

antidiabetic medications (including insulin), based on the degree of glucose control achieved with the addition of metreleptin to pre-existing diabetic therapy.

In clinical weight loss studies investigating the use of metreleptin in obese patients, injection site reactions were the most common adverse event (erythema, pruritus, inflammation, urticaria and edema). All sites of injection (abdomen, arm and leg) used for the site of injection were affected. Other adverse events mentioned in the Investigator's Brochure are headache, fatigue and flu-like symptoms, weight loss, alopecia and nausea. All these effects occurred with no relationship to dosing.

factors as to why these two particular subjects developed neutralizing antibodies. A third subject currently under investigation appears to have developed the neutralizing antibody after the study termination. It is common for patients receiving peptide therapeutics to develop antibodies against the treatment. Serum samples from 22 lipodystrophic patients, whose metreleptin exposure ranged from 3 months to 27 months, in a different research study using metreleptin in lipodystrophic patients (FHA101, MB002-002) have been tested for neutralizing antibodies. None of these patients' samples showed evidence of developing neutralizing antibodies at the time of the submission to the FDA.

It is our expectation that the assay for neutralizing antibody may change and our understanding of this phenomenon may evolve during the course of the study.

Serum will be saved from each visit to determine the levels of antibodies to Metreleptin. These assays are available through **Amryt**. The antibody assays will be run at yearly intervals after enrollment of the 6th patient. However, serum leptin levels can be used as a surrogate for the development of worrisome neutralizing activity since serum leptin level became undetectable in the two patients in whom neutralizing activity was demonstrated.

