### *Study Inclusion:*

Criteria for continuation into the long-term phase is based solely on proven clinical benefit using criteria universally accepted to be beneficial. The following criteria are accepted as evidence of substantial clinical benefit upon completion of CLINICAL PROTOCOL to investigate the efficacy of recombinant human leptin (METRELEPTIN) in nonalcoholic steatohepatitis (NASH) or nonalcoholic fatty liver disease (NAFLD) associated with lipodystrophy, MB002-014 (IRMBED: HUM00058708):

- Reduction of HbA1c  $\geq$ 1.0% or,
- Reduction of triglycerides  $\geq$ 30% of baseline or,
- Decrease in insulin requirements  $\geq$ 40% or,
- Reduction in total NASH score by  $\geq$ 2 points.
- Significant worsening of metabolic parameters after discontinuation of Metreleptin if discontinuation has been undertaken.

- A health condition that appears to have significantly improved by metreleptin for which two independent health care providers make a request to prevent drug discontinuation. In addition, the PI has to document absence of contraindications for drug continuation (such as bone marrow suppression).

*Study group:* We will enroll up to a total of up to 15 subjects to receive study drug Metreleptin from our parent studies.

*Restorative leptin therapy:* This is defined as administration of recombinant methionyl-human leptin subcutaneously to achieve high normal levels of circulating leptin in individuals who started out with lower than normal or low normal levels of circulating leptin(1, 2). Recombinant human leptin will be provided by Amryt Pharma (Boston, MA). Previous experience from patients with lipodystrophy or with congenital absence of leptin indicates that this goal can be achieved by administration of 0.02 to 0.10 mg/kg/day in adult males depending on baseline leptin concentrations and body surface area of the patients. In this study, patients will be treated with 2.5 and 5 mg /day (male and female respectively) to achieve high physiological concentrations. Higher dose titrations can be used in the judgment of the PI as indicated up to 10 mg daily. It is important to note that the patients enrolling in this long term study will be on metreleptin therapy that has been found effective, therefore, their dose will likely not change during this protocol. .

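### The yearly antibody assays wait for a sixth patient whom the protocol does not guarantee, and there is no fallback for the stored serum

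*Protocol*

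**What the plan says.** Section 4.2 of the protocol treats neutralizing antibodies as a named risk of metreleptin and makes three statements about watching for them.

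- Collection: "Serum will be saved from each visit to determine the levels of antibodies to Metreleptin". The assays are available through the drug supplier.
- Timing: "The antibody assays will be run at yearly intervals after enrollment of the" sixth patient.
- Surrogate: "serum leptin levels can be used as a surrogate for the development of worrisome neutralizing activity", on the ground given next: "since serum leptin level became undetectable in the two patients in whom neutralizing activity was demonstrated".

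On numbers, the study group paragraph under Study Inclusion says "We will enroll up to a total of up to 15 subjects", and the Treatment paragraph repeats that ceiling. Neither gives a minimum. The inclusion criteria admit only patients who completed one named parent protocol (MB002-014) and who meet a benefit criterion. Each patient is followed for five years with visits every six months. Section 1 makes long-term safety part of the aim.

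**The concern.** The reason to test is exposure to the drug, but the rule for starting depends on how many people have joined. Patients arrive already on metreleptin, so exposure accumulates from the first enrolment, while the assay clock starts only at the sixth. A study that can only recruit from the completers of one parent protocol, and that sets no minimum, may not reach six.

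At stake is whether the serum collected for this purpose is tested at all in a small study, and how soon the first patients' results are known in a larger one. A plan that names the risk, stores the samples and has a laboratory route should not leave the testing to a recruitment count. The leptin sentence follows the assay rule directly, so it is also worth asking whether leptin could carry the burden if the trigger were never met.

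**Working it through.** The protocol gives no calculation on this point, so there is no figure to reproduce. The check is of the rule, with a few supporting numbers.

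**1. Can the trigger fail?** Inputs: trigger at patient 6 (section 4.2); maximum 15, minimum not stated (Study Inclusion, Treatment). Possible enrolment therefore runs from 0 to 15.

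- Five or fewer enrolled: the condition is never met and no assay is triggered.
- Six to 15 enrolled: yearly assays start.

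The size of the eligible pool is not given, so the probability of the first case cannot be computed.

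**2. Does another section supply a fallback?** The follow-up paragraph lists fasting leptin but no antibody test. Section 2.3 B names several stored markers, and antibodies are not among them. Protocol Table 1 has a leptin row and no antibody row. Section 7 provides a yearly review by the Study Monitor but orders no assay. No fallback was found in the available text.

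**3. How much serum is affected?** Visits per completer = 1 baseline + 5 years × 2 per year = 11.

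- Five completers: 5 × 11 = 55 samples.
- Fifteen completers: 15 × 11 = 165 samples.

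**4. How long is the delay if six or more enrol?** Let D be the months from first to sixth enrolment, which the protocol does not give. The first patient's baseline serum waits D months if the first run is made at the trigger, or D + 12 if it is made a year later. The text allows either. If D exceeded 60 months, the first patient would finish the five years before any run. The serum would still be in storage, so the result would be late and not lost.

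**5. What would testing five patients give?** For 0 positives in n patients, the exact two-sided 95% upper limit is 1 − 0.025^(1/n).

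- n = 5: 1 − 0.025^(1/5) = 52.2%.
- n = 15: 1 − 0.025^(1/15) = 21.8%.

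The chance of at least one case is 1 − (1 − p)^n. The true rates p below are assumptions.

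| p | n = 5 | n = 15 |
|---|---|---|
| 5% | 22.6% | 53.7% |
| 10% | 41.0% | 79.4% |
| 20% | 67.2% | 96.5% |

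Five patients could not give a useful rate. They could still reveal a case, and that is what would be forgone.

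**6. Can leptin stand in?** Evidence given: 2 of 2 patients with neutralizing activity had undetectable leptin. The exact two-sided 95% lower limit for sensitivity is 0.025^(1/2) = 15.8%. This only puts a number on the fact that n is two, which the protocol states openly.

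**The case against.** The strongest reply is that little is likely to be lost. The study plans for up to 15, and nothing in the protocol suggests that five or fewer is expected. The sentence on saving serum states its purpose without condition, so an investigator might test it anyway. Waiting for a few patients may simply be batching. Leptin is measured at every six-month visit, more often than a yearly assay, and can serve as an interim signal. Section 5.7 requires reports of lack of efficacy, including decreased effect, and an independent Study Monitor reviews data yearly. No antibody rate is among the stated outcomes, and section 2 describes the study as close to expanded access.

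Most of this stands as a limit on size. It does not supply the missing fallback: a stated purpose for the serum is not a schedule for testing it, and leptin and efficacy reports are indirect.

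Three stronger readings are tempting, and the documents do not support them.

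- A reader might infer that the study will probably end without antibody data. That needs both an enrolment of five or fewer and stored serum left untested.
- A reader might infer that leptin replaces the assay, or that patients with detectable leptin will be counted as antibody-negative. The sentence says only that leptin can be used; it does not cancel the yearly assays, and no section classifies patients in that way.
- A reader might press the third possible case ("A third subject currently under investigation appears to have developed the neutralizing antibody after the study termination") or the 22 patients tested elsewhere ("None of these patients' samples showed evidence of developing neutralizing antibodies at the time of the submission to the FDA") against the surrogate, because no leptin values appear for them. The text just before this account is absent from the copy at hand, so that silence cannot be held against the plan.

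**Conclusion.** The point holds in a limited form. The start of antibody testing is tied to a sixth enrolment that nothing guarantees, and the available text has no fallback. With five or fewer patients the rule as written triggers no assay, leaving up to 55 stored samples untested if five complete. With six or more, the effect is delay for the earliest patients, by D to D + 12 months, and no loss. Leptin, supported by two patients, is reasonable as an additional signal and too thinly supported to fill the gap alone.

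This rests on reading the trigger literally, and on the absent part of section 4.2 containing no separate assay rule. The probability of enrolling five or fewer is unknown. No primary or secondary outcome is affected. The case for acting is that long-term safety is part of the aim and that the rule is cheap to improve.

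**What to change.** In section 4.2, delete the sixth-patient condition. State instead that stored serum from every enrolled patient, including the first five and any who leave early, will be assayed for antibodies at yearly intervals whatever the final enrolment. Add that serum leptin is a supportive signal and does not substitute for the assay.

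No extra visit or blood draw is needed: the serum is already saved at each visit and the assay route through the supplier exists. The cost is a few more assay runs, some in smaller batches. The protocol gives no assay price, so that cost cannot be put in figures. Sample size and outcome analyses do not change.

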#### **4.3 ADEQUACY OF PROTECTION FROM RISKS**

A) Recruitment and Informed Consent Procedures. Informed consent will be obtained from study patients by a member of the research team during the baseline visit prior to the initiation of the study protocol. This will be a face-to-face session with the patient and adequate time will be spent to go over the study and to answer the questions. If potential patients so desire, we will provide them with a copy of the current IRB approved consent and assent documents in advance of the baseline visit, either by mail, email or fax. Recruitment procedures and waiver of HIPAA rules for research recruitment will be overseen and approved by University of Michigan's IRB overseeing the research study.

#### B) Protection Against Risk

Care will be taken to protect the patient from any untoward risks through the entire study period. Patients' privacy will be protected based on HIPAA rules. Recruitment procedures and waiver of HIPAA rules for research recruitment will be overseen and approved by University of Michigan's IRB overseeing the research study. Informed consent documents contain detailed information on personal information of subjects and how these will be protected.

IRB application. This study protocol will be submitted to the University of Michigan IRBMED for initial approval. No patient recruitment, study activity, or any other activity with potential patients will be conducted until the study is approved by the IRBMED. The IND for use of Metreleptin for the purpose of this study is filed with the FDA with number 72,734.

#### **4.4 EARLY SUBJECT DISCONTINUATION**

Subjects may be removed from the study prior to completion for the following reasons:

1. Withdrawal of Consent: Subject wishes to exercise the right to withdraw from the study as stated in the ICF (all subjects reserve the right to withdraw from the study without prejudice).
2. Adverse Event: Subject experiences an AE that, in the investigator's opinion, necessitates withdrawal from the study.
3. Investigator Decision: Investigator feels it is in the subject's best interest to terminate participation for reasons other than an AE.
4. Protocol Violation: Subject is noncompliant with protocol procedures, becomes pregnant, violates study entry criteria, or starts an unacceptable concomitant medication.
5. Lost to Follow Up: Subject fails to return for study visits and cannot be reached with reasonable, repeated attempts.
6. Administrative Reason: The FDA or University of Michigan IRBMED regulatory authority discontinues the study protocol or the clinical study site discontinues participation.

#### **5. MONITORING FOR SIDE-EFFECTS AND ADVERSE EVENTS:**

Subjects will be screened for occurrence of side-effects at each visit. The laboratory data will be monitored by the study team as well as anonymously presented to an independent Study Monitor.

### 5.1 ADVERSE EVENTS DEFINITION

An Adverse Event (AE) is defined as any new untoward medical occurrence or worsening of a pre-existing medical condition in a patient or clinical investigation subject administered an investigational (medicinal) product and that does not necessarily have a causal relationship with this treatment. An AE can therefore be any unfavorable and unintended sign (including an abnormal laboratory finding, for example), symptom, or disease temporally associated with the use of investigational product, whether or not considered related to the investigational product (ICH Guidelines for Clinical Safety Data Management: Definitions and Standards for Expedited Reporting, Federal Register May 9, 1997).

Adverse events can be spontaneously reported or elicited during open-ended questioning, examination, or evaluation of a subject. (In order to prevent reporting bias, subjects should not be questioned regarding the specific occurrence of one or more AEs.)

All adverse events reported spontaneously by the subject, as well as those noted by the investigator or study site staff, are to be recorded. In order to avoid vague, ambiguous, or colloquial expressions, the adverse event term should be recorded using standard medical terminology rather than the subject's own words. Every attempt should be made to describe the adverse event in terms of a diagnosis. Whenever the investigator is confident in making a unifying diagnosis, all related signs, symptoms and abnormal test results should be grouped together and recorded as a single adverse event.

All subjects who have adverse events, whether or not the adverse events are considered associated with the use of the study medication, must be monitored until the adverse event resolves, stabilizes, or becomes chronic. The clinical course of the adverse event will be followed according to accepted standards of medical practice, even after the end of the observation period, until a satisfactory explanation for the adverse event is found or the investigator considers it medically justifiable to terminate follow-up.

All adverse events will be evaluated for intensity and causal relationship with use of the study medication.

The most frequently reported adverse events in studies of Metreleptin AC164594 have been skin reactions (injection site reactions) at the site where the drug is injected. These reactions include bruising, redness, pain, itching, inflammation, swelling, dark spots on skin, and lumps under the skin. Other frequently reported adverse events have been hypoglycemia (reported mainly in patients using insulin), decreased weight, hair loss, headache, fatigue, nausea and influenza-like symptoms. There may be additional risks such as potential allergic reaction to the study drug. There have been less frequent reports of generalized rashes, hives, and in rare instances, swelling of the lips and eyes. Further information on the adverse event profile may be found in the AC164594 Investigator's Brochure.

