*Treatment:* Up to fifteen patients will be enrolled into this long-term treatment extension study. Patients will be continued on metreleptin treatment as mentioned. This will be injected subcutaneously after reconstitution once a day in the morning at approximately the same time of the day that fits the subject's calendar. Dose may be titrated up to 15 mg daily based on metabolic response as needed.

*Follow-up schedule and monitoring:* Scheduled outpatient visits will occur at 6 month intervals. Tolerability will be assessed at each visit. During each visit, patients', weights, BMI, injection site inspection and basic laboratory data (comprehensive metabolic panel (fasting glucose, BUN, creatinine, sodium, potassium, chloride, CO2, calcium, total protein, albumin, total bilirubin, AST, ALT, alkaline phosphatase), fasting insulin, fasting leptin levels, fasting lipid panel (total cholesterol, triglycerides, HDL, LDL)), will be recorded. Throughout the study, lab work for CBC with differential count and creatinine kinase will be obtained at each visit.

Unscheduled visits may occur at more frequently than ever six months in order to follow-up on any adverse event or unanticipated health issues participants may be having.

*Study Termination:* Patient participation will be concluded five years after the patient's baseline appointment. At this time normal follow-up study procedures will be conducted, final drug accountability will be performed and patient will be transitioned to clinical care.

*Preparation for study visits:* Subjects will be asked to refrain from alcohol or tobacco use for 72 hours prior to the visit. They will report to the Research Center after 10 hours of fasting. They will be allowed to consume water overnight prior to the studies.

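### The bar on asking about any specific adverse event makes no exception for known risks, so mild hypoglycemia between six-monthly visits is likely to be under-recorded (low severity)

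*Protocol*

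**What the plan says.** Section 5 sets the general duty: "Subjects will be screened for occurrence of side-effects at each visit". Section 5.1 sets the permitted methods: "Adverse events can be spontaneously reported or elicited during open-ended questioning, examination, or evaluation of a subject". It then adds in parentheses, with prevention of reporting bias as the reason, that "subjects should not be questioned regarding the specific occurrence of one or more AEs". On recording, the same section says: "All adverse events reported spontaneously by the subject, as well as those noted by the investigator or study site staff, are to be recorded".

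The follow-up paragraph in section 2.2 gives the timing: "Scheduled outpatient visits will occur at 6 month intervals. Tolerability will be assessed at each visit". The same paragraph lists inspection of injection sites and fasting laboratory work, including glucose, at each visit, and allows unscheduled visits to follow up adverse events. On duration: "Patient participation will be concluded five years after the patient's baseline appointment".

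On known risks, section 4.2 states: "Hypoglycemia was the most frequent treatment-emergent adverse event reported in two previous clinical studies in 29 subjects with lipodystrophy". It also has investigators monitor subjects with diabetes and consider changes to antidiabetic medication. Section 5.1 names injection-site reactions as the most frequent events across metreleptin studies. It lists hypoglycemia among the other frequent events, mainly in insulin users.

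**The concern.** Long-term safety is part of the aim in section 1, and section 2.4 expects safety data as a result. A rule on how events are elicited determines what enters the database, so a later analysis plan cannot repair it. Here the rule removes targeted questioning for every event, including the one that section 4.2 ranks first in this disease.

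Two things are at stake. First, the recorded frequency of mild hypoglycemia may be too low. Second, the event profile may be uneven: one known reaction is looked for at every visit, while another depends largely on a general question about the preceding six months. The relative frequencies of the two would then partly reflect how each was sought. The independent Study Monitor's yearly review (section 7) relies on the same data.

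**Working it through.** The plan gives no figure on this point, so there is nothing to reproduce. The check has three steps.

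**1. How much of follow-up the scheduled laboratory work covers**

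Inputs from the follow-up and termination paragraphs of section 2.2: one visit every 6 months, 5 years per patient, fasting glucose at each visit.

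- Follow-up visits: 5 years ÷ 0.5 years = 10. With baseline, 11 scheduled glucose values.
- Days: 5 × 365.25 = about 1,826.
- Days with a scheduled glucose value: 11 ÷ 1,826 = 0.6%.

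A transient low glucose between visits will rarely be caught by scheduled laboratory tests.

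**2. Which route would find a mild episode that resolved between visits**

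| Route | Where | Finds such an episode? |
|---|---|---|
| Spontaneous report | 5.1 | Only if the patient raises it |
| Open-ended question at the visit | 5.1 | Possibly; the question does not name hypoglycemia |
| Examination or evaluation, events noted by staff | 5.1 | Possibly, if it emerges while subjects with diabetes are monitored (4.2) |
| Visit laboratory tests | 2.2, 5.8 | Rarely (step 1) |
| Unscheduled visit | 2.2 | Only if the episode prompts one |
| Serious adverse event reporting | 5.3, 5.4 | No; it covers serious episodes |
| Question naming hypoglycemia | 5.1 | Barred |

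The text available sets no method or frequency for monitoring glucose between visits and no targeted question. Part of section 4.2 was not available to read, so further monitoring text there cannot be excluded.

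For injection-site reactions, the table would gain one active row: direct inspection at every visit.

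**3. Whether an amount can be given**

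If the true rate of mild episodes is r and a fraction c of them is captured, the recorded rate is c × r. The routes above make c less than 1 likely, which gives the direction. The documents state neither r nor c, so the shortfall cannot be computed.

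**The case against.** **Other routes exist.** A reader might infer that hypoglycemia is counted only if volunteered. The text does not support that. Section 5.1 allows open-ended questioning, examination and evaluation, and it records events noted by staff. An open question is itself a prompt. Serious episodes (5.4), clinically significant laboratory results (5.8) and unscheduled visits (2.2) add further capture. This objection stands, and it narrows the point to mild episodes that resolved between visits.

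**No contradiction.** A reader might also infer that section 5 orders screening while section 5.1 forbids it. Screening and tolerability assessment can both be carried out with an open question, examination and laboratory tests, so the sections are compatible. This also stands.

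**The bar has a reason.** Suggestive questions can inflate absolute counts even without a comparator, and a single-arm study has no control rate to reveal it. That is a fair argument against leading questions. It is weaker against neutral, fixed questions asked after the open one and reported separately.

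**Limited relevance.** The study enrols up to 15 patients already on treatment whose dose is expected to stay stable. It is described as close to expanded access and has no hypoglycemia endpoint. Hypoglycemia is said to occur mainly in insulin users. This lowers the severity but does not remove the point: safety remains in the aim, and one entry criterion is a fall in insulin requirements, so insulin users can be expected.

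**The contrast with injection sites is partial.** Inspection sees only what is present that day, and transient site reactions between visits rely on the same open question. This is correct, and it is why the fix covers both reactions.

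**Conclusion.** The concern holds in a narrow form. Section 5.1 bars questions about any specific adverse event without an exception for named risks, and with six months between visits this makes under-recording of mild hypoglycemia likely. The direction is supported; the amount is not. A reader might be tempted to put a multiple on the shortfall by assuming an episode rate and a recall window. At a constant rate that multiple is simply the visit interval divided by the assumed window, so the assumption supplies the answer. It would also count nothing from open questioning, evaluation or unscheduled visits for episodes outside that window.

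The conclusion assumes that some patients have mild episodes that leave no trace at the next visit, that a non-specific question recalls fewer of them than a specific one, and that the unavailable part of section 4.2 does not override the bar. Severity is low: the plan is workable as written, and the change is a cheap improvement to data that cannot be recovered afterwards.

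**What to change.** Replace the parenthetical bar in section 5.1 with a two-step procedure:

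1. Ask the open question first and record the answer as spontaneous or openly elicited.
2. Then ask a short, non-leading set of questions, worded identically at every visit, on the known reactions in sections 4.2 and 5.1. Cover at least hypoglycemia and injection-site reactions since the last visit.

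Flag events found only at step 2 as solicited on the adverse event page, and tabulate them separately from spontaneous events. The order and the flag largely preserve the spontaneous data and answer the protocol's reporting-bias concern.

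The cost is one protocol sentence and a short checklist, used at no more than 15 × 10 = 150 scheduled follow-up visits. The downside is that solicited rates run higher and cannot be compared with spontaneous rates from earlier studies; the separate tabulation keeps a spontaneous count available for that purpose.
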